##### MRD after 3 years of maintenance and after maintenance “on demand”

Molecular residual disease (MRD) after 3 years of maintenance and after maintenance “on demand” will be evaluated. Assessment of MRD will be based on molecular level in BM according to EU MCL network guidelines. Patient without MRD assessment (due to whatever reason) will be considered as MRD positive.

This endpoint will be analyzed on efficacy set (ES).

#### 3.2.2.4 Secondary efficacy endpoint 4

##### PFS

PFS is defined as the time from inclusion into the study to the first observation of documented disease progression or death due to any cause. If a subject has not progressed or died, PFS will be censored at the time of last visit with adequate assessment.

This endpoint will be analyzed on efficacy set (ES) and on safety set (SS).

#### 3.2.2.5 Secondary efficacy endpoint 5

##### OS

Overall survival will be measured from the date of inclusion to the date of death from any cause. Alive patients will be censored at their last contact date.

This endpoint will be analyzed on efficacy set (ES) and on safety set (SS).

### 3.2.2.6 Secondary efficacy endpoint 6

#### **Stem cell collection failure**

Stem cell collection failure will be evaluated after induction.

This endpoint will be analyzed on efficacy set (ES) and on safety set (SS).

### 3.2.2.7 Secondary efficacy endpoint 7

#### **Duration of MRD negativity**

Duration of MRD negativity is defined as the time from the date of attainment the first negative MRD to the date of positive MRD. Duration of MRD negativity would be assessed for patients with at least one MRD negativity and as survival endpoint. For patients achieving a negative MRD but who have not positive MRD or not MRD assessment at the time of analysis, duration of MRD negativity will be censored on the date of last MRD assessment.

This endpoint will be analyzed on efficacy set (ES).

### 3.2.3 Secondary safety endpoints

Summary of study drug administration including treatment duration and average dose will be displayed.

Number, frequency, reasons for premature treatment discontinuation and study discontinuation will be summarized.

Adverse events, clinical laboratory measurements will be described.

AEs will be classified using the latest version of Medical Dictionary for Drug Regulatory Activities (MedDRA) coding system at the time of database lock. The severity of the toxicities will be graded according to the National Cancer Institute (NCI) Common Terminology Criteria for Adverse Events (CTCAE) whenever possible. Subsets of AEs to be summarized include serious, NCI CTCAE grade severities, suspected treatment-related, and events that resulted in withdrawal of investigational product. The most severe grade of each preferred term for a patient will be utilized for summaries of adverse events by NCI CTCAE grade.

All AEs and SAEs will be described by system organ class and preferred term (a patient having the same event more than once will be counted only once) by period. Focus on AEs leading to death, AEs leading to discontinuation from treatment and AEs of special interest (i.e Tumor Lysis Syndrom) will also be displayed in a separate table and listing.

All deaths will be listed and summarized by cause of death and narratives of death will be also presented.

This endpoint will be performed on safety set (SS).

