6.2 Secondary objectives

Secondary objectives are:

- To evaluate the efficacy of the Obinutuzumab in patients with MCL treated by DHAP before ASCT, after ASCT and every 6 months in terms of clinical response (Cheson 99) and MRD plus in terms of FDG-PET before and after ASCT

[figure not shown]
- To evaluate PFS, Overall survival at study end
- To evaluate the incidence of stem cell collection failure after obinutuzumab-DHAP = GA-DHAP
- To evaluate MRD negativity after 3 years of maintenance and after maintenance “on-demand”
- To evaluate PET result after 3 years of maintenance
- To evaluate duration of MRD negativity
- To evaluate tolerability of Obinutuzumab at induction and then “on-demand” (safety analyses)

Exploratory objective is :

- To determine baseline prognostic factors on PFS and OS.

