14.3 Serious Adverse Events reporting rules

All events that meet one or more criteria of seriousness (see Section 13.1.2.) will be reported **continuously** from the date of informed consent signature to 28 days after the last study drug administration of the maintenance period. During maintenance on-demand, if GA101 is discontinued (temporarily or permanently), SAEs will be reported until 28 days after last study drug administration. If GA101 is reintroduced (according to MRD results), SAEs will further be reported according to the same reporting rules.

SAE will be reported regardless:

- the relationship to the study treatment
- the administration of new lymphoma therapy,
- disease progression.

Nevertheless, the following SAEs that occur during maintenance on-demand beyond 28 days after the last administration of GA101 will be reported as SAEs regardless relationship to study treatment:

- Death
- Life-threatening events
- Severe infections, hepatitis, progressive multi-focal encephalopathy
- Cardiac events
- Neutropenia

To note that all SAEs **considered related to the study medication** will **always** be reported even if occur beyond 28 days after the last administration of GA101 including during the follow-up period.

Whenever possible, symptoms should be grouped as a single syndrome or diagnosis. The investigator should specify the date of onset, intensity, action taken regarding the study medication, corrective therapy given, outcome of all SAEs and his/her opinion as to whether the SAE can be related to the IMP.

General SAE reporting rules:

- Any episode of any grade of toxicities, which meets one of the seriousness criteria must be reported as "Serious Adverse Event" in the appropriate SAE form
- Signs, symptoms and physical findings indicative of lymphoma or progression of lymphoma are not to be reported as "Serious Adverse Event"
- Hospitalizations **not to be considered** as SAE are:
 - Planned hospital admissions or surgical procedures for an illness or disease which existed before the patient was enrolled in the study or before the study drug was given are not to be considered SAEs unless the condition deteriorated in an unexpected manner during the study (eg surgery was performed earlier than planned).
 - A procedure for protocol therapy administration or protocol/disease-related investigations. Hospitalization or prolonged hospitalization for a complication will be reported as an SAE

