#### 3.1.2 Secondary objectives

The secondary objectives of the study are:

- To evaluate the efficacy of the obinutuzumab in patients with MCL treated by DHAP before ASCT, after ASCT and every 6 months in terms of clinical response (Cheson 99) and MRD plus in terms of FDG-PET before and after ASCT
- To evaluate PFS, Overall survival at study end
- To evaluate the incidence of stem cell collection failure after obinutuzumab-DHAP = GA-DHAP
- To evaluate MRD negativity after 3 years of maintenance and maintenance “on-demand”
- To evaluate PET results after 3 years of maintenance
- Duration of MRD negativity
- To evaluate tolerability of obinutuzumab at induction and then “on-demand”

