## 5.10 Safety analysis

### 5.10.1 Adverse Events

**Table 5.101-1 Summary of AEs – Safety set**

	Induction N=XX	ASCT N=XX	Maintenance N=XX	Total N=XX
Patients with at least one AE				
No	XX (XX.X%)	XX (XX.X%)	XX (XX.X%)	XX (XX.X%)
Yes	XX (XX.X%)	XX (XX.X%)	XX (XX.X%)	XX (XX.X%)
If yes, number of Aes by patients				
N	XX	XX	XX	XX
Missing	XX	XX	XX	XX
Mean (SD)	XX.X (XX.XX)	XX.X (XX.XX)	XX.X (XX.XX)	XX.X (XX.XX)
Median	XX.X	XX.X	XX.X	XX.X
Q1 ; Q3	XX ; XX	XX ; XX	XX ; XX	XX ; XX
Min ; Max	XX ; XX	XX ; XX	XX ; XX	XX ; XX
Patient with at least one AE of grade >= 3				
No	XX (XX.X%)	XX (XX.X%)	XX (XX.X%)	XX (XX.X%)
Yes	XX (XX.X%)	XX (XX.X%)	XX (XX.X%)	XX (XX.X%)
Patient with at least one fatal AE				
No	XX (XX.X%)	XX (XX.X%)	XX (XX.X%)	XX (XX.X%)
Yes	XX (XX.X%)	XX (XX.X%)	XX (XX.X%)	XX (XX.X%)
Patient with at least one AE leading to treatment discontinuation				
No	XX (XX.X%)	XX (XX.X%)	XX (XX.X%)	XX (XX.X%)
Yes	XX (XX.X%)	XX (XX.X%)	XX (XX.X%)	XX (XX.X%)
Patient with at least one AESI*				
No	XX (XX.X%)	XX (XX.X%)	XX (XX.X%)	XX (XX.X%)
Yes	XX (XX.X%)	XX (XX.X%)	XX (XX.X%)	XX (XX.X%)

\* AESI = Tumor Lysis Syndrom and IRR grade 4 occuring during or within 24 hours after the GA101 infusion.

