**Table 5.101-2 Summary of related AEs – Safety set**

	Induction N=XX	ASCT N=XX	Maintenance N=XX	Total N=XX
Patients with at least one related AE				
No	XX (XX.X%)	XX (XX.X%)	XX (XX.X%)	XX (XX.X%)
Yes	XX (XX.X%)	XX (XX.X%)	XX (XX.X%)	XX (XX.X%)
If yes, number of related Aes by patients				
N	XX	XX	XX	XX
Missing	XX	XX	XX	XX
Mean (SD)	XX.X (XX.XX)	XX.X (XX.XX)	XX.X (XX.XX)	XX.X (XX.XX)
Median	XX.X	XX.X	XX.X	XX.X
Q1 ; Q3	XX ; XX	XX ; XX	XX ; XX	XX ; XX
Min ; Max	XX ; XX	XX ; XX	XX ; XX	XX ; XX
Patient with at least one related AE of grade >= 3				
No	XX (XX.X%)	XX (XX.X%)	XX (XX.X%)	XX (XX.X%)
Yes	XX (XX.X%)	XX (XX.X%)	XX (XX.X%)	XX (XX.X%)
Patient with at least one fatal related AE				
No	XX (XX.X%)	XX (XX.X%)	XX (XX.X%)	XX (XX.X%)
Yes	XX (XX.X%)	XX (XX.X%)	XX (XX.X%)	XX (XX.X%)
Patient with at least one related AE leading to treatment discontinuation				
No	XX (XX.X%)	XX (XX.X%)	XX (XX.X%)	XX (XX.X%)
Yes	XX (XX.X%)	XX (XX.X%)	XX (XX.X%)	XX (XX.X%)
Patient with at least one related AESI*				
No	XX (XX.X%)	XX (XX.X%)	XX (XX.X%)	XX (XX.X%)
Yes	XX (XX.X%)	XX (XX.X%)	XX (XX.X%)	XX (XX.X%)

\* AESI = Tumor Lysis Syndrom and IRR grade 4 occuring during or within 24 hours after the GA101 infusion.

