**Table 5.101-3 AEs by SOC and PT – Safety set**

	Safety set N=XX
AEs	XX (XX.X%)
SOC 1	XX (XX.X%)
PT 1	XX (XX.X%)
PT ...	XX (XX.X%)
SOC ...	XX (XX.X%)
PT 1	XX (XX.X%)
PT ...	XX (XX.X%)

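### The adverse-event tables do not carry out the SAP's own by-period rule and give no incidence for on-demand obinutuzumab, although its tolerability is a secondary objective

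*SAP*

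**What the plan says.** Both documents list the objective: "To evaluate tolerability of Obinutuzumab at induction and then" on demand (Protocol 6.2), and "To evaluate tolerability of obinutuzumab at induction and then" on demand (SAP 3.1.2).

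SAP 3.2.3 gives the rule for reporting: "All AEs and SAEs will be described by system organ class and preferred term", with "a patient having the same event more than once will be counted only once) by period". Protocol 15.1.2.2 has the same rule. The population is the Safety Set, meaning everyone who received at least one dose of obinutuzumab (SAP 4.4.4).

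Under Protocol 10.2.3, maintenance is one injection every 2 months for 3 years. On-demand treatment is given on days 1, 8 and 15 of the first month and then monthly, and only to MRD-positive patients. MRD-negative patients in the same period receive no drug.

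On collection, Protocol 14.3 says that when GA101 is stopped during the on-demand phase, "SAEs will be reported until 28 days after last study drug administration". It then lists SAE categories that are still reported after that limit.

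**The concern.** An objective that names a treatment phase needs output for that phase. If the shells are followed as drawn, on-demand events are either pooled into the Maintenance column, which mixes two schedules, or appear only in Total. The SAP does not say which. In both cases a reader cannot take from any table the proportion of re-treated patients who had a grade 3 or higher, a related or a fatal event, or see which events these were.

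The denominator matters too. The on-demand period contains treated and untreated patients, and the Safety Set also contains patients who never reached it. A count set against either group is not an incidence in the exposed.

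**Working it through.** The point concerns table structure. The plan states no figure to reproduce, so the check sets the rule against each shell.

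| SAP output | Period dimension | On-demand shown? |
|---|---|---|
| Table 5.101-1, "Patients with at least one AE" and related rows | Induction, ASCT, Maintenance, Total | No |
| Table 5.101-2, "Patients with at least one related AE" and related rows | Same four columns | No |
| Table 5.101-3, "AEs by SOC and PT" | None; one Safety Set column | No |
| Table 5.101-4, AEs by SOC/PT and highest intensity | None; columns are grades 3, 4, 5 | No |
| Table 5.102-2, SAE summary | None | No |
| Both tables numbered 5.102-3, SAEs and related SAEs by SOC/PT | None | No |
| Tables 5.101-5 and 5.102-4, characteristics | Onset-period rows | Yes, one row each, under the Safety Set N |
| Discontinuation table (SAP 5.2.1) and death table (SAP 5.10.4) | Period rows | No |

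**Is on-demand meant to be part of Maintenance?** The two characteristics tables list them as separate periods, and Table 5.9-5 gives on-demand its own exposure output. The SAP therefore treats them as distinct elsewhere, and the AE summaries do not say what their Maintenance column contains.

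**What do the characteristics tables give?** They have rows for intensity, relationship to GA101 and outcome, including fatal. These rows are not crossed with onset period and carry no terms. The shells also do not say whether patients or events are counted.

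**What can be recovered by hand?** Listings 5.10.1-1 (fatal AEs), 5.10.1-2 (AEs leading to discontinuation), 5.10.1-3 (AESI) and 5.10.2-2 (SAEs) carry the event period, as does Listing 5.9-1 for AEs with GA101 interrupted. The dose N in Table 5.9-5 may give the number treated on demand. The remainder is non-serious grade 3–4 AEs that are not AESI and neither stopped nor interrupted GA101. The AE pages mainly collect grades 3–5 (Protocol 14.2), so this remainder is a substantive part of what is recorded.

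**Illustration of the denominator.** The number re-treated is not in the documents. On-demand treatment is limited to patients with informative baseline MRD, so the planned 70 evaluable patients are used as the base. The Safety Set is taken as 70 to 83 (SAP 4.1: 70 evaluable, about 83 enrolled). Assume 5% to 25% of 70 are re-treated:

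- 0.05 × 70 = 3.5, about 4 patients; 0.25 × 70 = 17.5, about 18 patients.
- Ratio of Safety Set N to re-treated n: from 70/18 = 3.9 to 83/4 = 20.8.
- Example at 20%: 0.20 × 70 = 14 re-treated, 6 with an event. 6/14 = 42.9% (90% Clopper-Pearson 20.6% to 67.5%); 6/70 = 8.6%; 6/83 = 7.2%.

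These figures show the effect of the denominator. They do not predict results, and no current shell would print the diluted percentage for grade 3 or higher on-demand events, because none crosses period with grade.

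**The case against.** The strongest reply is that the rule already exists. SAP 3.2.3 requires output by period and the onset coding names on-demand as a period, so a programmer who follows the text would produce what is needed. The summary tables also carry a separate N in each column, so period-specific denominators may be intended. This is fair as far as it goes: the fault is a mismatch between text and shells, not a wrong method. It does not remove the point, because the shells are what will be programmed and they contradict the text.

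A reader might infer three stronger things that the documents do not support.

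- *That the objective cannot be answered at all.* The listings and Table 5.9-5 supply much of the serious-event information.
- *That most patients in the on-demand phase are off drug.* The only related figure, under 20% MRD-positive at later time points (Protocol 11.3.1), is a share of samples in other studies. The share of patients ever re-treated over 3 years of 3-monthly testing could be higher.
- *That events in untreated patients go uncollected.* Beyond 28 days, Protocol 14.3 still requires deaths, life-threatening events, severe infections, hepatitis, PML, cardiac events and neutropenia as SAEs whatever the relationship, and all related SAEs.

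It is also true that the plan specifies the Safety Set for safety. A re-treated denominator is a refinement that the objective calls for, not something the plan promised.

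**Conclusion.** The point holds as an internal contradiction. The SAP text requires SOC/PT tables by period; none of the SOC/PT shells has a period, and the AE summaries omit the phase that the objective names. Following the shells would leave non-serious grade 3–4 on-demand events largely unattributable to that phase, and would give no tabulated incidence among re-treated patients.

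The size cannot be stated from the documents. The 4- to 21-fold range rests wholly on the assumption that 5% to 25% of 70 patients are re-treated. The structural finding does not depend on it.

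The primary endpoint is unaffected. The shells should be corrected before the final analysis, when all secondary endpoints are due (SAP 4.3).

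**What to change.** 1. Add a maintenance on-demand column to Tables 5.101-1 and 5.101-2, and give the SAE summary (Table 5.102-2) the same column.
2. In that column, restrict both the numerator and N to patients with at least one on-demand GA101 dose. Show MRD-negative, untreated patients in the period separately: some of their SAEs are still collected, and would otherwise enter a numerator without being in the denominator. State where events before a patient's first on-demand dose are counted.
3. State that the Maintenance column excludes on-demand events.
4. Produce the SOC/PT tables for AEs (including by grade), SAEs and related SAEs by period, as SAP 3.2.3 requires.
5. Add on-demand to the period rows of the discontinuation table (SAP 5.2.1) and the death table (SAP 5.10.4).

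The cost is extra columns and rows in existing shells. Onset period is already a variable in the characteristics tables and on-demand dosing is already summarised in Table 5.9-5, so no new data and no change to patient management are needed.

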### 3.2.4 Exploratory endpoints

The following exploratory endpoint will be summarized using appropriate statistical methods.

#### **Baseline prognostic factors on PFS and OS**

A dedicated analysis on survival (PFS/OS) will be performed in order to determine baseline prognostic factors. The implemented method will take into account the specificities of on-demand treatment during the second maintenance period.

### 3.3 Follow-up duration

The follow-up duration is defined as the time between the inclusion date and the last contact date. Follow-up duration is based on OS and calculated with a reverse Kaplan-Meier method. Deceased patients are censored at the date of death.

### 3.4 Extent of exposure

- Treatment duration
- Total dose
- % planned dose

## 4 STATISTICAL CONSIDERATIONS

### 4.1 Sample size calculation

#### Hypothesis:

We expect to have an increase of 15% of the MRD negativity in bone marrow (BM) rate for patients treated with GA-DHAP.

Based on the interim results of LYMA presented at ASH 2014, the MRD negativity rate were 65% (Legouill, ASH 2014). Nevertheless, in the LYMA study, the MRD has been assessed after 4 cycles of DHAP only for patient that completed the 4 cycles. Therefore this rate does not take into account the rate of patients who progressed on treatment or took R-CHOP because of insufficient response. If we take into account these patients considering them as non responder patients and based on the LYSA/LYSARC experience, then the MRD negativity rate of all patients in the LYMA may be around 55%. Considering that these patients will also be included in the LyMa101 we have to take into account a rate of 55% of MRD negativity instead of 65% in the sample size calculation.

The hypotheses are as follows:

- Experimental treatment will be considered ineffective if the MRD negativity in BM after the 4 cycles or at treatment discontinuation (at a molecular level) proportion is  $\leq 55\%$  ( $P_0$ )
- Experimental treatment will be considered effective if the MRD negativity in BM after the 4 cycles or at treatment discontinuation (at a molecular level) proportion  $\geq 70\%$  ( $P_1$ )
- $\alpha$  risk of 0.05 and  $\beta$  of 0.20
- one-sided test

Patients will be considered as MRD positive if the patient has no MRD assessment due to whatever the reason.

#### Sample Size:

A total of 70 evaluable patients will be required for this study. Assuming that some included patients will not receive the treatment or will not be informative for MRD in bone marrow and/or blood at baseline, enrollement will be done until 70 patients are evaluable. For this purpose, about 83 patients should be enrolling (15% drop-out).

Sample size calculation was performed using an exact single-stage phase II design with East 5.4 (A'Hern RP. Sample size tables for exact single-stage phase II designs. Stat Med. 2001. 20(6):859-66).

### 4.2 Primary criterion analysis

This analysis will be performed once all patients included in efficacy set (70 patients) have completed the 4 cycles of treatment or treatment discontinued prior to cycle 4 and will consist of analyzing:

- Primary criterion : MRD negativity in BM rate after the 4 cycles or at treatment discontinuation of GA-DHAP
- Treatment exposure
- Stem cell collection failure
- Secondary safety endpoints

Among the 70 evaluable patients, if 46 patients or more have a MRD negativity after the 4 cycles or at treatment discontinuation the treatment will be considered as sufficiently effective and further investigations (another trial) will have to be foreseen.

## 4.3 Final analysis

This analysis will be performed when all included patients will undergo the end of treatment visit (at end of maintenance “on demand” period or at treatment discontinuation) and will consist of the whole statistical analyses.

At this time all secondary and exploratory endpoints will be analyzed.

## 4.4 Analysis Sets

### 4.4.1 Included Set (IS)

The included set will include all included patients having signed the informed consent.

### 4.4.2 Efficacy Set (ES)

The Efficacy set will include all patients having signed the informed consent, received at least one dose of the IMP study drug (Obinutuzumab) and with an informative MRD in BM and/or blood at baseline.

### 4.4.3 Modified Efficacy Set (mES)

The modified Efficacy Set will include all patients having signed the informed consent, received at least one dose of the IMP study drug (Obinutuzumab), with an informative MRD in BM and/or blood at baseline and an informative MRD in BM after the 4 cycles of GA-DHAP or at treatment discontinuation.

### 4.4.4 Safety Set (SS)

The Safety set will include all patients having signed the informed consent and received at least one dose of the IMP study drug (Obinutuzumab).

## 4.5 General statistical approach

### 4.5.1 Statistical analysis

Continuous data will be summarized in tables displaying number of observations, mean, standard deviation, median, range; quartiles will also be presented when considered relevant.

Categorical data will be expressed as frequencies and percentages (of non-missing data).

Response rates (according to Cheson 1999 or MRD) will be expressed with 90% confidence limits (to be consistent with one sided 5% level of significance) according to Pearson-Clopper method. The number and percent of patients falling into each category of response will be provided.

Time to event will be performed using Kaplan-Meier method. Survival probabilities, median survival and quartiles will be estimated with their 95% CI. Survival curves will be provided. A dedicated analysis on survival (PFS/OS) will be performed in order to determine baseline prognostic factors. The implemented method will take into account the specificities of on-demand treatment during the second maintenance period.

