#### 4.5.2 Statistical methods

Unless otherwise noted, statistical tests will be two-sided and performed using a 5% level of significance.

The Kaplan Meier method, also known as the "product-limit method", is a non-parametric method for estimating the probability of survival at any given point in time. The kaplan-meier method handles both censored and uncensored data.

The log-rank test is a non-parametric test for comparing the survival distributions of two or more groups. This test is computed using the expected and observed number of events in each group.

Cox proportional-hazard model is a semi-parametric model used for testing differences in survival times of two or more groups of interest, while allowing to adjust for covariates of interest.

Chi-square test is used to test equality of proportions between two or more populations and is computed by comparing the observed and expected counts when the null hypothesis is true.

The Wilcoxon rank-sum test, also called Mann–Whitney *U* test, is a non-parametric test used to compare distributions from two independent groups and assess whether one has systematically larger values than the other.

The independent samples T-Test is a parametric test used to compare the means of a normally distributed variable for two independent groups.

Logistic regression is a regression model in which the outcome is a categorical variable. The log odds of the outcome are modeled as a linear combination of the predictor variables.

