## 5.7 Efficacy Analysis

### 5.7.1 Primary efficacy analysis

#### 5.7.1.1 Main analysis

**Table 5.7.1.1-1 MRD results on BM after induction or at treatment discontinuation – Efficacy Set**

	ddPCR N=XX	Q-PCR N=XX
MRD after induction		
Negative	XX (XX.XX%)	XX (XX.XX%)
Positive	XX (XX.XX%)	XX (XX.XX%)
Positive < 10E-04	XX (XX.XX%)	XX (XX.XX%)
Missing	XX (XX.XX%)	XX (XX.XX%)
MRD negativity rate*		
Negative	XX (XX.XX%)	XX (XX.XX%)
IC 95%	[XX.XX% - XX.X%]	[XX.XX% - XX.X%]

\* Patients without MRD assessment are considered as Positive MRD

**Listing 5.7.1-1 Patients with missing MRD results on BM after induction or at treatment discontinuation – Efficacy Set (XX patients)**

Patient identification number	Inclusion date	Last period	Patient suitable for MRD monitoring	MRD after Induction	
				Interpretation on PB	Interpretation on BM
XXXXX	XX/XX/XX	XX	XX	XX	XX

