#### 5.7.1.2 Sensitivity analysis

**Table 5.7.1.2-2 MRD results on BM after induction or at treatment discontinuation – modified Efficacy Set**

	ddPCR N=XX	Q-PCR N=XX
MRD after induction		
Negative	XX (XX.XX%)	XX (XX.XX%)
Positive	XX (XX.XX%)	XX (XX.XX%)
Positive < 10E-04	XX (XX.XX%)	XX (XX.XX%)
MRD negativity rate		
Negative	XX (XX.XX%)	XX (XX.XX%)
IC 95%	[XX.XX% - XX.X%]	[XX.XX% - XX.X%]

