### 5.7.4 Response rate

Table 5.7-6 Response according to Cheson 99 – Efficacy Set

		Evaluation after 3 years of maintenance N=XX	End of treatment N=XX
Response (Cheson 99)			
Complete Metabolic Response		XX (XX.X%)	XX (XX.X%)
Partial Metabolic Response		XX (XX.X%)	XX (XX.X%)
No Metabolic Response		XX (XX.X%)	XX (XX.X%)
Progressive Metabolic Disease		XX (XX.X%)	XX (XX.X%)
Not Evaluated		XX (XX.X%)	XX (XX.X%)
Overall Response Rate (ORR)			
Patients with ORR		XX (XX.X%)	XX (XX.X%)
IC 95%		[XX.X% - XX.X%]	[XX.X% - XX.X%]
Overall Response Rate* (ORR)			
Patients with ORR		XX (XX.X%)	XX (XX.X%)
IC 95%		[XX.X% - XX.X%]	[XX.X% - XX.X%]

\* Patients who relapsed or died during treatment phase are considered as non-responders even if they were responders before withdrawal.

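### The plan specifies 90% Clopper-Pearson limits for MRD and Cheson response rates, but every SAP table shell that prints an interval for them labels it 95%

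*SAP*

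**What the plan says.** The level, the method and the reason for the level are stated three times, in agreement: in the protocol synopsis (Analysis Plan), in protocol section 15.4 and in SAP section 4.5.1. The SAP wording is that such rates "will be expressed with 90% confidence limits (to be consistent with one sided 5% level of significance"); the method it names is Clopper-Pearson. The same SAP section gives 95% limits to time-to-event estimates only.

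The test behind this is one-sided with alpha 0.05 and beta 0.20, against a null MRD-negativity rate of 55% and an alternative of 70% (protocol 15.2, SAP 4.1). The success rule is in SAP 4.2: "Among the 70 evaluable patients, if 46 patients or more have a MRD negativity", the treatment is considered sufficiently effective.

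The SAP shells that print an interval for these rates are:

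- Table 5.7.1.1-1, bone-marrow MRD, Efficacy Set: one interval row, with ddPCR and Q-PCR columns. Its footnote reads "Patients without MRD assessment are considered as Positive MRD".
- Table 5.7.1.2-2, "MRD results on BM after induction or at treatment discontinuation", modified Efficacy Set: one interval row, same two columns.
- Section 5.7.4, Cheson response table, Efficacy Set: two ORR interval rows. The second belongs to the analysis footnoted "Patients who relapsed or died during treatment phase are considered as non-responders even if they were responders before withdrawal".
- Section 5.7.4, the same table for the Safety Set: two ORR interval rows.

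All six rows are labelled IC 95%.

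**The concern.** The methods text and the shells give different levels for the same intervals, and one of the shells is the primary efficacy table. Shells are what programmers build from, so the 95% label could well be what reaches the report, against the level fixed in protocol version 5.0 (04/04/2018).

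The 90% level has a stated purpose: the two-sided interval should correspond to the one-sided 5% test. A two-sided 95% interval corresponds to a one-sided 2.5% test instead. At counts that pass at 5% but not at 2.5%, the primary table would show an interval that includes the null rate next to a statement that the treatment is sufficiently effective. A reader who takes the interval as the test would draw the opposite conclusion from the plan's own rule.

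**Working it through.** **Inputs.** Null 55%, alternative 70%, one-sided alpha 0.05, beta 0.20, 70 evaluable patients (protocol 15.2, SAP 4.1); success at 46 or more (protocol 15.5, SAP 4.2); Clopper-Pearson method (SAP 4.5.1).

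**Reproducing the plan's design.** With X binomial(70, p):

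- Alpha = P(X ≥ 46 | p = 0.55) = 0.0452.
- Power = P(X ≥ 46 | p = 0.70) = 0.8201.
- A search for the smallest n with exact alpha ≤ 0.05 and power ≥ 0.80 returns n = 70 with cut-off 46, which is the plan's figure.

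**Limits.** For x of n at level 1 − a, the Clopper-Pearson limits are beta quantiles: lower = Beta(a/2; x, n − x + 1), upper = Beta(1 − a/2; x + 1, n − x). With n = 70:

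| x | Rate | Rule met | One-sided exact p vs 55% | 90% limits | 95% limits |
|---|---|---|---|---|---|
| 45 | 64.3% | no | 0.0738 | 53.8 to 73.8% | 51.9 to 75.4% |
| 46 | 65.7% | yes | 0.0452 | 55.3 to 75.1% | 53.4 to 76.7% |
| 47 | 67.1% | yes | 0.0262 | 56.8 to 76.4% | 54.9 to 77.9% |
| 48 | 68.6% | yes | 0.0143 | 58.3 to 77.7% | 56.4 to 79.2% |

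The 90% lower limit exceeds 55% from 46 upward, so it agrees with the rule at every count. The 95% lower limit exceeds 55% only from 48 upward, so it disagrees at 46 and 47.

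**How often this would arise.** At a true rate of 70%, P(X = 46) + P(X = 47) = 0.0742 + 0.0884 = 0.1627. As a share of trials that meet the rule, 0.1627 / 0.8201 = 19.8%. The chance depends on the true rate: 19.3% at 65%, 5.6% at 75% and 0.6% at 80%.

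**Effect of reading success from the 95% interval.** The cut-off would in effect be 48, with alpha = P(X ≥ 48 | 0.55) = 0.0143 and power = P(X ≥ 48 | 0.70) = 0.657, against the planned 0.05 and 0.80.

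**Width at 46/70.** 95%: 76.65 − 53.40 = 23.25 points. 90%: 75.11 − 55.29 = 19.82 points. Ratio 23.25 / 19.82 = 1.17, so the labelled interval is about 17% wider than the specified one.

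**Does another SAP clause authorise 95%?** Section 4.5.2 says "Unless otherwise noted, statistical tests will be two-sided and performed using a 5% level of significance". That sentence concerns tests, and it gives way where something else is noted. Section 4.5.1 does note something else, for exactly these rates, so the default does not supply a 95% level here.

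**Shells not affected.** The peripheral-blood MRD tables (5.6.3-1 and 5.6.3-2), the later bone-marrow MRD table (5.7.6-1) and the table of response after treatment for relapse (section 5.8) print no interval. The 95% limits for PFS and OS agree with section 4.5.1.

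**The case against.** The strongest reply is that little follows from the label. Success is a count, no clause makes an interval the criterion, and the methods text already tells the programmer what to produce. The two Cheson tables test no null and the modified Efficacy Set table has no success rule of its own, so any tension with the decision rests on one row of one table. Even there, a 95% interval that includes 55% does not logically contradict a pass at one-sided 5%; it answers a stricter question. The 16.3% holds only at a true rate of 70% and an Efficacy Set of exactly 70. Finally, the documents contain empty shells: the primary analysis was planned for Q1 2019, when SAP version 1.0 (11JAN2019) was the listed version, and neither that version nor any output can be seen.

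Most of this stands as a limit on the size of the problem. There is no decision error, the hazard is misreading rather than a wrong test, and whether a 95% interval was ever reported is unknown. None of it removes the discrepancy. The text and the shells cannot both be followed, and the stated purpose of the 90% level is the agreement with the test that the 95% label loses at 46 and 47.

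**Conclusion.** The concern holds. All six interval rows in the four shells carry a level that the protocol and SAP text do not specify for these rates. The decision rule, its alpha of 4.5% and its power of 82.0% are untouched. In the primary table, the labelled interval would include the 55% null at 46/70 and 47/70 although the rule is met. In the other three tables the effect is only an interval at an unplanned level, about 17% wider than specified if the count were 46/70.

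The result at 46 and 47 assumes the Clopper-Pearson method named in the SAP and exactly 70 patients in the Efficacy Set. With a Wald or Wilson 95% interval, only 46/70 would include 55% (lower limits 54.6% and 54.0% at 46; 56.1% and 55.5% at 47). This should be fixed, because it affects the primary output and costs almost nothing to correct.

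**What to change.** Replace the IC 95% label with 90% CI (Clopper-Pearson) in Tables 5.7.1.1-1 and 5.7.1.2-2, for both assay columns, and in the two ORR rows of each Cheson response table in section 5.7.4. Set the matching output option. Keep the 46-of-70 rule. Because the 90% level is already in protocol version 5.0, this restores a pre-specified level and is not a post-hoc choice, even though SAP version 2.0 is dated 09OCT2024. If 95% intervals have already been reported, show the 90% intervals beside them and say which level was planned.

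The cost is six row labels in four shells, with no new data.

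One optional and separate addition: because "enrollement will be done until 70 patients are evaluable", the Efficacy Set could exceed 70. In that case the exact one-sided binomial p-value against 55% at the realised size could also be reported, for whichever assay is designated primary. It would be descriptive and set no new success rule. Any size other than 70 is an assumption here. An exact 5% test at such a size may have power just under or over 80%: 79.8% at 71 (cut-off 47), 77.4% at 72 (cut-off 48) and 82.2% at 73 (cut-off 48).
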